| Nausea | 22.3 | 14.9 | 15.7 | 8.4 | 17.8 | 20.3 |
| Pruritus | 15.7 | 4.3 | 12.0 | 6.1 | 18.3 | 19.2 |
| Insomnia | 14.0 | 7.5 | 12.2 | 5.1 | 15.4 | 18.0 |
| Diarrhea | 13.5 | 9.0 | 8.7 | 11.4 | 14.4 | 16.9 |
| Asthenia | 13.5 | 6.7 | 9.0 | 3.9 | 13.9 | 12.8 |
| Rash | 10.0 | 5.9 | 6.2 | 3.7 | 11.1 | 14.5 |
| Cough | 8.7 | 5.1 | 6.7 | 4.7 | 11.5 | 11.0 |
| Irritability | 5.3 | 4.7 | 3.2 | 3.1 | 7.2 | 12.2 |
| Anemia | 5.3 | 0 | 7.5 | 0.2 | 7.7 | 10.5 |
| Dyspnea | 9.7 | 5.5 | 4.7 | 2.2 | 5.8 | 12.2 |
| Laboratory Events, % | N = 765 | N = 254 | N = 401 | N = 509 | N = 208 | N = 172 |
| Hemoglobin | | | | | | |
| < 10 g/dL (Gr 2) | 5.5 | 0 | 6.2 | 0 | 7.2 | 11.0 |
| < 8.0 g/dL (Gr 3) | 0.1 | 0 | 0.5 | 0 | 1.4 | 0.6 |
| ALT | | | | | | |
| > 5 \times ULN (Gr 3) | 1.2 | 3.9 | 0.7 | 0.2 | 2.9 | 0 |
| Bilirubin | | | | | | |
| > 3 \times ULN (Gr 3) | 2.6 | 0 | 5.7 | 0.4 | 13.5 | 5.2 |

wk = week, PBO = placebo

Note: Percentages of laboratory events are based on the number of subjects with at least one post-baseline value.

Transient elevations in total (predominantly indirect) bilirubin have been observed, due to ABT-450 inhibition of the bilirubin transporters OATP1B1 and OATP1B3 and RBV-induced hemolysis. The elevations generally peaked by Weeks 1 and 2, declined through the end of treatment and returned to within the normal range by 4 weeks

post-treatment. Hyperbilirubinemia occurred less frequently in subjects treated with 3 DAAs without RBV compared to 3 DAAs with RBV. The frequency and degree of hyperbilirubinemia were higher in subjects with cirrhosis, but the temporal pattern of elevation followed by resolution was similar and few episodes were symptomatic. Grade 2 + hemoglobin reductions occurred in 6% of subjects without cirrhosis who received the 3-DAA + RBV regimen for 12 weeks, and 7% and 11% of subjects with cirrhosis who received the 3-DAA + RBV regimen for 12 and 24 weeks, respectively. Grade 3 hemoglobin values were rare. The decline in hemoglobin was largely managed with RBV dose reductions. Anemia observed during the clinical trials was largely attributable to the presence of RBV as it was not observed when the 3-DAA regimen was administered without RBV.

Transient asymptomatic postbaseline serum ALT elevations of $> 5 \times$ ULN occurred at a frequency of 1% across active treatment arms and were evaluated by an external hepatic panel. The ALT elevations were asymptomatic, usually occurred within the first 4 weeks of treatment and typically declined with ongoing treatment. A disproportionate number of the cases were in women on concurrent systemic estrogen-containing therapy (i.e., contraceptives or hormone replacement) and discontinuation of the hormonal therapy with continuation or brief interruption of the DAA regimen led to resolution in serum ALT elevation. Concomitant use of systemic estrogen-containing medications is a risk factor for these postbaseline elevations in serum ALT. No ALT elevations $> 5 \times$ ULN were observed in subjects receiving progestins only or in subject receiving topical vaginal estrogen preparations. Among the cases of serum ALT elevation thought to be related to the DAA regimen, none resulted in hepatic dysfunction and they generally resolved or improved with ongoing treatment. All cases had resolved completely in the post-treatment follow-up.

ABT-450/ritonavir and ABT-267 (and its major inactive human metabolites) had no effects on embryo-fetal development in rodent and/or nonrodent species at maximal feasible exposures that provided AUC multiples at least 4-fold higher than exposure at the

recommended clinical doses. Clinical studies in women who are pregnant have not been conducted.

The current study is intended to offer subjects with genotype 1 HCV infection who experience virologic failure in a previous AbbVie/Abbott DAA combination study an optional intensified treatment regimen. This study will assess the safety, antiviral activity and resistance profile of ABT-450/r 200/100 mg QD and ABT-267 25 mg QD combined with pegIFN and RBV in subjects who met a virologic failure criterion in a previous study. Among subjects who previously experienced null or partial response to pegIFN/RBV treatment (with or without approved DAAs) at any time prior to pre-screening for this study, or who experienced virologic failure with pegIFN/RBV plus telaprevir in the prior AbbVie/Abbott study, enrollment will be limited to only those subjects in whom variants in HCV NS3/4A protease and NS5A at amino acid residues known to be associated with resistance are not present at a pre-screening visit. Subjects who never experienced prior null or partial response to pegIFN/RBV treatment, and who never experienced virologic failure with pegIFN/RBV plus telaprevir in the prior AbbVie/Abbott study, will be allowed to enroll in Study M13-101 at the discretion of the investigator, regardless of whether resistant variants are detected.

3.1 Differences Statement

The differences between previous DAA combination studies in HCV-infected subjects and this study are as follows:

The current study, Study M13-101, is a single arm study evaluating ABT-450/r in combination with ABT-267, pegIFN and RBV for 24 weeks followed by pegIFN and RBV alone for an additional 24 weeks in subjects who have experienced virologic failure in a previous AbbVie/Abbott DAA combination study. None of the previous AbbVie/Abbott DAA combination studies included pegIFN with both ABT-450 and ABT-267 in the treatment regimen, or explored efficacy of a DAA, pegIFN and RBV containing regimen in subjects who previously failed a DAA-based therapy.

3.2 Benefits and Risks

Risk of Toxicity

The toxicity profile of pegIFN and RBV has been well described and includes headache, myalgia, fatigue, pyrexia, injection site reactions, and cytopenias. Previous studies of pegIFN and RBV in combination with ABT-450/r (Study M11-602) or ABT-267 (Study M12-114) demonstrated that the safety profiles of the respective regimens were generally comparable to those of pegIFN and RBV alone. In contrast, combination dosing of ABT-450/r with ABT-267 has generally been well tolerated both in healthy volunteers and both with and without RBV for up to 12 weeks in HCV-infected subjects (based on ongoing studies). Preclinical toxicology studies have assessed the toxicity of ABT-267 for up to 6 months, and ABT-450 for up to 9 months. ABT-450 and ABT-267 have been administered in clinical trials for up to 24 weeks. Subjects who enroll in Study M13-101 after having completed > 12 weeks of prior combination therapy may ultimately receive ABT-450/r and ABT-267 cumulatively for more than 24 weeks; thus there is also a risk of toxicity due to administration longer than 24 weeks that has not previously been observed. However, no dose-limiting toxicities have thus far been observed in animal studies, or in humans receiving the doses of ABT-450/r and/or ABT-267 used in this study. ABT-450/r and ABT-267 have not previously been dosed together in combination with pegIFN and RBV.

Risk of Treatment Failure

The likelihood of successfully curing HCV-infected subjects with a regimen containing 2 DAAs + pegIFN + RBV after they have previously failed therapy with DAA combination therapy is not known. A previous study by Bristol Myers-Squibb used the NS5A and protease inhibitors BMS-790052 and BMS-650032¹⁰ in combination with pegIFN and RBV in prior pegIFN/RBV null responders and achieved a high rate of virologic suppression. Subjects who experience virologic failure in this study are at risk of selecting HCV variants with resistance to up to 3 classes of DAA (depending on their prior DAA combination therapy), which may compromise future treatment options if the variants persist off treatment. However, it is assumed that many of these subjects will

already have selected resistance to one or more DAA class in the setting of their prior treatment failure. Therefore, the risk of incurring a greater degree of viral drug resistance (and the resulting loss of additional treatment options) must be weighed against the possible benefit of an efficacious treatment regimen. Since this balance may be different depending on multiple factors (including prior treatment experience, stage of liver disease, other available treatment options, IL28B host genotype and others), this study will be made available on a purely optional basis to all subjects who previously experienced virologic failure in an AbbVie/Abbott DAA combination trial. It is expected that subjects will make a decision regarding participation in consultation with the investigator. However, since prior non-responders (null or partial response) to pegIFN/RBV may have a suboptimal response to a second course of pegIFN and RBV, this population will only be eligible if population sequencing of HCV NS3/4A protease and NS5A from a sample collected at the Pre-screening Visit does not detect variants at positions known to be associated with reduced susceptibility to ABT-450 and ABT-267. Likewise, even subjects who had an initial response to pegIFN/RBV plus telaprevir or boceprevir and then failed (due to relapse or breakthrough) may, in fact, be poor responders to interferon, and the initial virologic response may have reflected suppression due to the protease inhibitor. Hence, subjects who received pegIFN/RBV plus telaprevir in the previous AbbVie/Abbott study will only be eligible if population sequencing does not detect ABT-450 or ABT-267 resistance-associated variants.

In summary, the risks associated with the individual study drugs to be administered in Study M13-101 have been well characterized and appear limited and manageable. Subjects will be closely monitored for any potential risks which may occur when the DAAs are dosed in combination, including risks of toxicity and of virologic failure. Given the potential benefit of achieving cure in a population of HCV-infected subjects with limited available treatment options, as well as the manageable risks associated with the planned therapy, the risk-benefit comparison is considered favorable.

4.0 Study Objective

4.1 Primary Objective

The primary objective of this study is to evaluate the safety and antiviral efficacy, defined as the percentage of subjects with sustained virologic response 12 weeks post-dosing (SVR₁₂; HCV RNA < LLOQ 12 weeks after the last dose of study drug).

4.2 Secondary Objectives

The secondary objectives of this study are:

- to evaluate the percentage of subjects with sustained virologic response 24 weeks post-dosing (SVR₂₄; HCV RNA < LLOQ 24 weeks after the last dose of study drug) and
- to evaluate the percentage of subjects with extended rapid virologic response (eRVR) (HCV RNA < LLOQ at Weeks 4 through 12 of therapy with ABT-450/r plus ABT-267 plus pegIFN plus RBV).

5.0 Investigational Plan

5.1 Overall Study Design and Plan: Description

[figure not shown]
This is a Phase 2, open-label, single arm combination treatment study of ABT-450/r and ABT-267 in combination with pegIFN/RBV in HCV genotype 1-infected subjects (including subjects with compensated cirrhosis) who have experienced virologic failure while participating in a previous AbbVie/Abbott DAA combination study. Among subjects who previously experienced null or partial response to pegIFN/RBV treatment at any time prior to pre-screening for this study, or who experienced any prior failure with pegIFN/RBV plus telaprevir in the previous AbbVie/Abbott study, enrollment in this study will be restricted to those in whom population sequencing at the Pre-screening Visit does not detect the presence of variants relative to the appropriate prototypic reference sequence (H77 for 1a or Con1 for 1b) at any of the following amino acid positions: NS3 155, 156, or 168; or NS5A 28, 29, 30, 31, 32, 58, or 93. All other subjects will be

allowed to enroll in Study M13-101 at the discretion of the investigator, regardless of whether variants at any of these amino acid positions are detected.

This study consists of a pre-screening period, a screening period and three substudies:

- Substudy 1 (Treatment Intensification [TI]): 24 weeks of therapy with ABT-450/r plus ABT-267 plus pegIFN plus RBV;
- Substudy 2 (PegIFN/RBV [PR] Treatment): 24 weeks of pegIFN and RBV therapy alone;
- Substudy 3 (Post-treatment [PT] Follow-up Period): 48 weeks after last dose of any study drug for resistance monitoring and HCV RNA viral load testing.

Figure 1. Study Schematic

This study is designed to assess the safety, antiviral activity and pharmacokinetics (PK) of the DAAs ABT-450/r plus ABT-267, dosed for 24 weeks in combination with pegIFN and RBV, followed by an additional 24 weeks of pegIFN and RBV alone. All subjects who receive at least 1 dose of DAA therapy in this protocol, regardless of whether they prematurely discontinue or complete the study drug as planned, will be monitored for viral response and viral resistance on an outpatient basis for an additional 48 weeks following the last dose of any study drug as described in Section 5.1.4.

5.1.1 Pre-screening

Subjects who receive at least 1 dose of DAA and who experience virologic failure either during DAA therapy (rebound, breakthrough or failure to suppress) or after the end of therapy (relapse) in a previous AbbVie/Abbott DAA combination study, will be offered enrollment in this study if the subject meets all of the eligibility criteria specified in Section 5.2.1 and Section 5.2.2, and if study drug therapy is considered medically appropriate based on the opinion of the investigator.

[figure not shown]
The Pre-screening Visit may be conducted at any time after the subject is confirmed failure from the previous AbbVie/Abbott DAA combination study. Once the subject is confirmed to meet all the eligibility criteria then the subject must discontinue from the previous AbbVie/Abbott DAA combination study. Subjects must provide written (signed and dated) informed consent for Study M13-101 prior to any study-specific procedures, including the population sequencing analysis done at the Pre-screening Visit. The investigator will record the details of the informed consent process in the subject's medical records. A blood sample will be collected for all subjects at the Pre-screening Visit for population sequencing of the HCV NS3/4A protease and NS5A genes. Another sample will be drawn at the same time at this visit to determine the HCV RNA level. The HCV RNA level must be at least 2000 IU/mL in order to perform the population sequencing testing. The Pre-screening Visit may be repeated at a later date per the investigator's discretion if the HCV RNA level is < 2000 IU/mL. Subjects will retain their subject number from the previous DAA combination study. This information will be entered into the Interactive Response Technology (IRT) system under the Pre-screening Visit flow. This number will be written on the Pre-screening Visit blood collection tubes and on the lab requisition form prior to shipping the samples to the central laboratory. The results of the population sequencing will take approximately 3 weeks to complete.

Among subjects who previously experienced null or partial response to pegIFN/RBV treatment at any time prior to pre-screening for this study, or who had any prior failure with pegIFN/RBV plus telaprevir in the previous AbbVie/Abbott study, enrollment will be limited to only those subjects in whom variants in HCV NS3/4A protease and NS5A at

amino acid residues known to be associated with resistance are not present at the Pre-screening Visit. All other subjects will be allowed to enroll in Study M13-101 at the discretion of the investigator, regardless of whether resistant variants are detected. If the results of population sequencing do not exclude the subject from participation, the subject should undergo a Screening Visit for this study as soon as possible. However, subjects will have up to 12 weeks after the Pre-screening Visit to perform the Screening Visit. If it is longer than 12 weeks, the site must get approval from the Study Designated Physician prior to conducting the Screening Visit. Refer to [Figure 2](#) for the Pre-screening Visit flow chart.

Subjects who do not meet inclusion criteria for HCV RNA level or who meet the exclusion criteria for resistance at the Pre-screening Visit must be entered into the IRT system as a Pre-screen failure under the Discontinuation Visit flow. Subjects with exclusionary resistance-associated variants detected at the Pre-screening Visit will not be allowed to repeat the Pre-Screening Visit.

Figure 2. Pre-screening Visit Flow Chart

5.1.2 Screening

Once the Investigator has established that the subject does not meet exclusion criteria No. 1 (by review of results of the Pre-screening resistance testing, if applicable), the Screening Visit can be performed. The subject will be entered into the Interactive Response Technology (IRT) system under the Screening Visit flow. The subjects will undergo the study procedures identified in [Table 5](#) and [Table 6](#) (for cirrhotic subjects).

The investigator will evaluate whether the subject meets all of the eligibility criteria specified in [Section 5.2.1](#) and [Section 5.2.2](#) during the period from the Screening Visit through TI Day 1 prior to dosing, capture the concomitant medication and record the results of all assessments in the subject's medical records. Eligible subjects have up to

42 days following the Screening Visit to enroll into the study. Prior to enrollment, subjects should agree to practice two effective methods of birth control while receiving study drugs starting with Study Day 1 and for 7 months after stopping study drug or as directed by the local ribavirin label. Subjects using systemic estrogen-containing contraceptive therapy (including estrogen-containing oral contraceptives) have a higher risk for elevated ALT levels. Subjects using these medications must discontinue them at least 2 weeks prior to study drug administration or 10 half-lives (if known), whichever is longer. Subjects may replace the systemic estrogen-containing contraceptive with a progestin-only hormonal contraceptive method.

Once the subject is confirmed to meet all the eligibility criteria then the subject must discontinue from the Post-Treatment Period of the previous AbbVie/Abbott DAA combination study.

Subjects who otherwise meet all eligibility criteria, but have a positive urine alcohol screen, may have only the urine drug screen repeated. If the repeat urine drug screen is qualifying (does not meet Exclusion Criterion No. 4), the subject may be considered eligible.

Subjects who meet all inclusion criteria and none of the exclusion criteria with the exception of one exclusionary lab parameter may rescreen once without prior AbbVie approval. AbbVie Study Designated Physician approval is required to rescreen a subject who has multiple exclusionary laboratory results. Subjects undergoing rescreening must repeat all laboratory tests that were initially out-of-range. Subjects who fail to enroll within 42 days of the Screening Visit may be allowed to rescreen only once without approval of the AbbVie Study Designated Physician and must be rescreened for all laboratory and eligibility criteria (with the exception of HCV genotype, Anti-HCV Ab, FSH, BDI-II Scale and fundoscopic exam). Liver ultrasound and alpha-fetoprotein testing for subjects with cirrhosis do not need to be repeated unless 6 months or more have elapsed since the initial screening.

Subjects with an exclusionary HCV genotype, exclusionary drug screen (other than a positive urine alcohol), positive anti-HIV antibodies or hepatitis B surface antigen, a Becks Depression Inventory II (BDI-II) score > 21 or positive pregnancy test will be excluded and may not rescreen.

Subjects who are not eligible to enroll per the inclusion/exclusion criteria after the Screening Visit must be entered into the IRT system as a screen failure under the Discontinuation flow.

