8. Discontinuation of antiviral therapy due to intolerance or a DAA- or RBV-associated adverse event in the previous AbbVie/Abbott DAA combination study (excluding intolerance or AEs associated with telaprevir).
9. Beck's Depression Inventory-II (BDI-II) score of > 21 at Screening. Subjects with BDI-II score > 21 will not be allowed to rescreen.
10. Clinically significant abnormal ECG, ECG with QT interval corrected for heart rate using Fridericia's correction formula (QTcF) > 470 msec at Screening or TI Day 1 visits.

11. Screening laboratory analyses show any of the following abnormal laboratory results:
- Alanine aminotransferase (ALT) $> 7 \times$ upper limit of normal (ULN);
 - Aspartate aminotransferase (AST) $> 7 \times$ ULN;
 - Calculated creatinine clearance (using Cockcroft-Gault method) < 60 mL/min;
 - Albumin $< LLN$;
 - International normalized ratio (INR) > 1.7 ; (Subjects with a known inherited blood disorder and INR > 1.7 may be enrolled with permission of the AbbVie Study Designated Physician.)
 - Hemoglobin $< LLN$;
 - Platelets $< 90,000$ cells per mm^3 ;
 - Absolute neutrophil count $< 1,500$ cells/ μL (< 1200 cells/ μL for subjects of black/African descent);
 - Indirect bilirubin $> 1.5 \times$ ULN and direct bilirubin $> ULN$;
 - Thyroid stimulating hormone (TSH) values outside the normal range.
12. The use of colony stimulating factors, such as granulocyte colony stimulating factor (GCSF) or erythropoietin within 2 months of the Screening Period.
13. Recent (within 6 months prior to study drug administration) history of drug or alcohol abuse that, in the opinion of the investigator, could preclude adherence to the protocol.
14. Clinically significant abnormalities, other than HCV infection, based upon the results of a medical history, physical examination, vital signs, laboratory profile and a 12-lead electrocardiogram (ECG) that make the subject an unsuitable candidate for this study in the opinion of the investigator.
15. Evidence of infection with other HCV genotypes other than genotype 1 at the Screening Visit.

16. Current enrollment in another clinical study or previous enrollment in this study. Concurrent participation in a non-interventional, epidemiologic or registry trials may be permitted with approval by the AbbVie Study Designated Physician.
17. History of solid organ transplantation.

In addition to Exclusion criteria 1 through 18, subjects with compensated cirrhosis must not meet the following criteria:

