| | Bicarbonate | Opiates ^a |
| | Magnesium | Barbiturates ^a |
| | Serum glutamic oxaloacetic transaminase/Aspartate aminotransferase (SGOT/AST) | Amphetamines ^a |
| | Serum glutamic pyruvic transaminase/Alanine aminotransferase (SGPT/ALT) | Cocaine ^a |
| | Gamma-glutamyl transferase (GGT) | Benzodiazepines ^a |
| | Creatinine clearance | Alcohol ^a |
| | TSH | Phencyclidine ^a |
| | Free T4 (performed for any abnormal TSH after screening) | Propoxyphene ^a |
| | Uric acid | Methadone ^a |
| | Alpha fetoprotein ^d | Human chorionic gonadotropin (hCG) (females) ^b |
| | | Total insulin ^c |
| | | HCV RNA |
| | | IP-10 |
| | | FSH (all females) ^a |
| | | HCV genotype and subgenotype ^a |

- a. Performed only at Screening.
- b. Urine pregnancy testing is not required after TI Day 1 Visit for female subjects with a documented prior hysterectomy or bilateral oophorectomy or bilateral tubal ligation or confirmed postmenopausal. Pregnancy testing post-treatment is to be completed per local label and/or local treatment guidelines and at a minimum at the visits detailed in [Table 7](#).
- c. Performed at TI Day 1 only.
- d. Tested for cirrhotic subjects only as indicated on [Table 6](#) and [Table 8](#).

For any laboratory test value after the subject has enrolled that is outside the reference range and the investigator considers clinically significant:

- The investigator will repeat the test to verify the out-of-range value.
- The investigator will follow the out-of-range value to a satisfactory clinical resolution.
- A laboratory test value that requires a subject to discontinue study drug or to be discontinued from the study, or that requires treatment, will be recorded as an adverse event.

The management of laboratory abnormalities that may occur during the study is described in Section 6.7.

BDI-II Depression Inventory

The Beck Depression Inventory will be completed by all subjects at Screening. Subjects with a score > 21 at the Screening Visit will not be enrolled. Subjects will not be allowed to retake the BDI-II unless rescreening is required due to more than 42 days elapsing since the initial screening procedures (due to reasons beyond the investigator's control).

Assignment of Subject Numbers

Subjects will retain their subject number from the previous AbbVie/Abbott DAA combination study and will enter the previous study number and subject number into the IRT system at the Pre-Screening Visit.

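### After a lapse of more than 42 days the protocol does not require a repeat BDI-II, so a subject can start pegIFN on a depression score with no stated age limit

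*Protocol*

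**What the plan says.** Protocol 5.1.2 gives eligible subjects up to "42 days following the Screening Visit to enroll into the study". Those who miss that window "may be allowed to rescreen only once without approval of the AbbVie Study Designated Physician", and their laboratory and eligibility checks are repeated "with the exception of HCV genotype, Anti-HCV Ab, FSH, BDI-II Scale and fundoscopic exam". The next sentence of 5.1.2 deals with liver ultrasound and alpha-fetoprotein in subjects with cirrhosis. These "do not need to be repeated unless 6 months or more have elapsed since the initial screening".

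5.1.2 also has a second route to rescreening, for exclusionary laboratory results. There the instruction is "Subjects undergoing rescreening must repeat all laboratory tests that were initially out-of-range".

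The BDI-II paragraph of 5.3.1.1 places the questionnaire at Screening and then restricts repetition: "Subjects will not be allowed to retake the BDI-II unless rescreening is required due to more than 42 days elapsing". The full condition reads "more than 42 days elapsing since the initial screening procedures (due to reasons beyond the investigator's control".

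Exclusion 9 (5.2.2) excludes a score above 21 at Screening and adds: "Subjects with BDI-II score > 21 will not be allowed to rescreen".

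**The concern.** The BDI-II threshold is an entry safeguard for a regimen containing up to 48 weeks of pegIFN, and 6.7.6 treats psychiatric symptoms on pegIFN as a matter for close monitoring. Depressive symptoms can change over weeks or months, unlike some other items on the exempt list, such as genotype. For a subject who enrols on time, the 42-day window limits the age of the score. For a subject rescreened after that window, the limit disappears for the BDI-II, although most other checks are refreshed.

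A score above 21 bars rescreening, so every rescreened subject already holds a passing score. A repeat could therefore only identify someone who has since crossed the threshold. That is the subject the present rule can miss. What is at stake is the safety of individual subjects, not any analysis.

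**Working it through.** The plan states no figure for the age of the score, so there is nothing to reproduce. The check is a comparison of the text, followed by simple date arithmetic.

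**1. Is a repeat required after a lapse?** 5.1.2 says no, because the BDI-II is on the exempt list. 5.3.1.1 is a prohibition with an exception:
- lapse beyond the investigator's control: retake allowed, not required;
- lapse for any other reason: retake barred on the wording.

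The two sections are compatible only if a retake is never mandatory.

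**2. Does anything else limit the age of the score?**
- Exclusion 9 tests the score at Screening and gives no validity period.
- Inclusion 7 asks whether the investigator considers the subject a suitable candidate for pegIFN.
- Exclusion 14 covers clinically significant abnormalities, including on medical history.
- 5.3.1.1 has the medical history updated through TI Day 1.
- 6.7.6 asks that past or current severe psychiatric conditions be weighed and managed before enrolment.

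These all rest on judgment. None asks for a current score. The 6-month rule for ultrasound and alpha-fetoprotein shows that the protocol provides for rescreening after a long gap and sets a time limit for those two tests, but not for the BDI-II.

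**3. How old can the score be at first dose?** Inputs: the 42-day window (5.1.2) and the 6-month case (5.1.2). Assumptions: 6 months = 183 days; the BDI-II is done on the day of the Screening Visit; the 42-day window restarts at rescreening. The age at TI Day 1 is the rescreening day plus the days then used, at most 42.

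| Case | Arithmetic | Age of score (days) |
|---|---|---|
| Never rescreened | window only | at most 42 |
| Lapse, rescreened on day 43 | 43 + 42 | 85 |
| Lapse, rescreened at 6 months | 183 to 183 + 42 | 183 to 225 |
| Laboratory-only rescreen on day 42, if that also restarts the window | 42 + 42 | 84 |

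The interval before rescreening is not capped, so the text sets no upper limit.

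**4. A less severe reading.** 5.1.1 allows 12 weeks (84 days) from Pre-screening to Screening without Study Designated Physician approval, and sequencing takes about 3 weeks (21 days). Suppose that limit also covers the rescreening visit and the first Screening Visit was on day 21. The largest age without approval is then 84 − 21 + 42 = 105 days. Approval is needed beyond that, and there is still no cap.

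**The case against.** The strongest reply is that this is a deliberate choice. The exemption is explicit, 5.3.1.1 provides for a retake in some cases, and nothing in the documents shows that a score older than 42 days is unsafe. The safeguards listed above are real: together they should catch newly emerged severe depression before dosing, and 6.7.6 requires study drug to stop for suicidal ideation. A second rescreening after a lapse needs Study Designated Physician approval. The 6-month case is inferred from a conditional clause about cirrhotic subjects, not from an expected delay. All of this stands, and it keeps the priority low. It does not supply an age limit or explain why a retake should depend on who caused the delay.

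Three stronger readings are tempting but not supported:

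- *That enrolling a subject whose score has since risen above 21 breaches Exclusion 9.* As written, Exclusion 9 applies to the score at Screening, and 5.1.2 waives its repetition. The gap is in the rule, not in compliance with it.
- *That repeating the BDI-II only after a lapse of more than 42 days would cap its age at 42 days.* If a laboratory-only rescreen also restarts the window, the score can reach 84 days by that route. The documents do not settle whether it does.
- *That the liver imaging and alpha-fetoprotein rule has the same defect.* It has a stated 6-month limit. How that limit combines with Inclusion 11 depends on the reading: if Inclusion 11 is re-applied at rescreening, a historical scan is at most about 91 + 42 = 133 days old at first dose (3 months taken as 91 days). Substituting a flat 6-month rule could loosen that, so no change is proposed.

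**Conclusion.** The point holds as an eligibility gap. After a lapse of more than 42 days, a repeat BDI-II is never required and is sometimes barred, and the score used at first dose has no stated age limit. The illustrative ages of 85 and up to about 225 days rest on the 42-day window restarting at rescreening and on 6 months being 183 days. The absence of an upper limit rests on the text alone.

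The practical reach is small. Only rescreened subjects among the up to 35 can be affected. The documents do not say how many there are, and there may be none. SVR12 and every other estimate and analysis are unchanged. The change is worth making because it is nearly free and tells sites plainly when a retake is due, but it is not a condition for the study to proceed.

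**What to change.** Make two edits to the protocol.

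1. In 5.1.2, delete the BDI-II from the list of tests exempt from rescreening.
2. In 5.3.1.1, replace the retake sentence with: *The BDI-II must be repeated at any rescreening if the last BDI-II would be more than 42 days old at TI Day 1, whatever the reason for the delay; the most recent score is used for Exclusion 9. It may not otherwise be retaken.*

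The trigger is the age of the score at TI Day 1, not the reason for rescreening, so both rescreening routes are covered whether or not a laboratory-only rescreen restarts the window. If the TI Day 1 date is not fixed at rescreening, the site should assume the last permitted day. The score is then at most 42 days old at first dose for every subject. The second sentence of the replacement text also makes Exclusion 9 apply to the repeat score. The bar on rescreening after a score above 21 stays, as do the imaging and alpha-fetoprotein rules.

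The cost is one short questionnaire, already used in the study, per affected subject. A subject who now scores above 21 would not be enrolled. The analysis plan needs no change.
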